4.6.2 Control Arm: Waitlisted Integrated Smoking Cessation and Financial Counseling

Six months after enrolling, participants randomized to the Control Group will receive all of the services described in the Intervention Group section above. Starting 3 weeks before their 6-month time point, study staff will call patients to schedule a counseling appointment (Appendix I). Patients in the control arm will not receive any procedures or counseling in the first six months.

4.6.3 Both Arms: Nicotine Replacement Therapy (NRT)

Participants in both arms will be eligible to receive a free four-week supply of NRT. Following the US Public Health Service guidelines for the treatment of persons who smoke ≥ 10 cigarettes per day, participants will receive combination NRT (patch plus gum or patch plus lozenge, depending on patient preference).⁵⁰ As we have done on other studies, we will order participants' NRT from drugstore.com after obtaining the participants' NRT preference during counseling. Drugstore.com will mail the NRT to our study office before the first counseling session. Counselors will provide the NRT and review proper use during the first session.

4.6.4 Both Arms: Patient Participant Follow-up Surveys

We will conduct a telephone follow-up survey 6 months (Appendix F) and 12 months (Appendix G) after enrollment with all participants. A study team member will make 10 attempts over 4 weeks to complete the survey (Appendix J). We will mail a hard copy or email the survey if participants do not want to complete the survey over the phone. The surveys will re-assess participant behavior and characteristic assessed at baseline, and a short series of close-ended and open-ended questions about satisfaction with the interventions. The first 150 participants will complete an additional 2 month follow up survey (Appendix E) in order to obtain preliminary data. After the first 150 enrollments, the 2 month survey will be retired and the remainder of the 450 enrollments will only complete surveys at baseline, 6 months and 12 months. All enrollees that signed a consent form indicating the additional 2 month survey will be eligible to participate in that survey and will be compensated accordingly. Participants will be paid \$15 as reimbursement for their time completing the surveys. The additional follow-up survey (Appendix S) to gain feedback from participants who are NYCHA-residents on their smoking cessation needs will be conducted via phone. Patients being contacted are already enrolled in the study.

4.6.5 Patient Participant Administrative Data

We will obtain written patient consent and HIPAA authorization to conduct review of their medical record to abstract data on health care utilization during the study. This will include total number of outpatient visits and total number of inpatient visits in the 12 months before and after their study enrollment. Staff will also check the EMR for updated contact info.

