2.3 Study Design

We will conduct a two-arm randomized, wait-list control study. We will recruit 610 participants total: 600 patient participants and 10 staff participants. We will recruit 600 smokers to complete a 9-week intervention that integrates financial management and smoking cessation counseling. Participants will be randomized (300 per arm, stratified by site) to receive the intervention immediately after enrolling (Intervention Arm) or 6 months later (Waitlist Control Arm). Both arms will receive nicotine replacement therapy (NRT) for four weeks as part of their time in integrative counseling. We will survey participants at baseline, 6 months and 12 months to assess outcomes and their satisfaction with treatment. The first 150 enrollees will complete an additional 2 month follow up survey. Additionally, we will recruit and interview hospital staff (N=5 per site, 10 total) to assess their perceptions regarding barriers and facilitators toward downstream implementation of the intervention.

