4. METHODS AND PROCEDURES

4.2 Patient Participant Recruitment

We will recruit patients using 5 methods. First, we will place flyers (Appendix A) in the waiting rooms of the primary care clinics and social work clinics at each hospital and at the elevator banks on each floor. We will also distribute flyer advertisements in the AM New York and Metro, two free local papers (Appendix Z) and El Especialito, a Spanish local paper (Appendix A). Flyers will describe the study, primary eligibility criteria, and a phone number to call. Patients who call will be screened for eligibility by a trained Research Assistant (RA) over the phone (Appendix C). The RA will schedule eligible participants for an in-person appointment to complete an IRB-approved informed consent process. Additionally, we will advertise on Facebook to English and Spanish speaking smokers located in New York City (Appendix A).

Second, this study will utilize NYUMC DataCore to use the Bellevue and NYU Lutheran's EMR data to identify patients who were screened as current tobacco users during a clinical visit in the

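### A single 12-month post-enrollment visit total mixes the controls' months before and after the programme is offered, so it cannot isolate the first-six-month effect on health care use

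*Combined protocol and SAP*

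**What the plan says.** Section 4.6.5 asks for consent to review the medical record and abstract health care use, including the "total number of outpatient visits and total number of inpatient visits in the 12 months before and after their study enrollment". No section asks for a count that stops at month 6.

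Section 4.6.2 sets the control schedule. For the first half-year, "Patients in the control arm will not receive any procedures or counseling in the first six months". After that, "Six months after enrolling, participants randomized to the Control Group will receive all of the services described in the Intervention Group section above". Section 2.3 starts the intervention arm at enrollment, gives the programme length as 9 weeks and plans 300 participants per arm.

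Section 5.1 models each outcome by arm, by time (baseline, 6 and 12 months) and by their interaction. It does not mention visits; its cost work concerns delivering the programme. Health care use is not among the aims in Section 1 or Section 2.2.

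**The concern.** The waitlist design offers one clean treated-versus-untreated window: months 0 to 6. After that both arms have been offered the same programme. The follow-up surveys have a reading at month 6, but the visit data, as described, do not. A single post-enrollment total per participant puts the clean window and the later one into the same number, and the total alone does not allow them to be separated. It also supplies no month-6 value for the Section 5.1 model, should visits be treated as one of its outcomes.

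Comparing the year before with the year after is not a safe substitute. The record-search route in Section 4.2 will "identify patients who were screened as current tobacco users during a clinical visit in the" preceding 12 months, and the waiting-room route approaches people who are attending a clinic. For people recruited in those ways the earlier count is raised by selection, and some fall afterwards is expected with no programme effect.

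At stake is what can be learned about health care use from a record review that participants are asked to authorize.

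**Working it through.** **Inputs from the documents.** Visit windows of 12 months before and after enrollment (4.6.5); controls untreated in months 0-6 and offered the programme from month 6 (4.6.2); 300 per arm (2.3). The documents give no visit rate, standard deviation, effect size, uptake, alpha or power for this measure, so there is no stated figure to reproduce. Everything numerical below is an assumption shown as a range.

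**Notation.** b = visits per six months without the programme; d1 = effect in the first six months after starting; d2 = effect in the following six months; p = the control arm's response in months 6-12 as a share of d1.

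**Arm difference in the 12-month total.**
- Intervention: 2b + d1 + d2
- Control: 2b + p × d1
- Difference: d2 + (1 - p) × d1

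With p = 1 this is d2 and d1 drops out. With p below 1 a share of d1 remains, but mixed with d2. With months 0-6 counted alone, the difference is (b + d1) - b = d1.

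**Signal-to-noise relative to the 0-6 month contrast.** With independent Poisson counts and a small effect, doubling the time multiplies the standard deviation by √2 = 1.414. The ratio is [d2/d1 + (1 - p)] / 1.414. If the two half-year counts have correlation r, the divisor becomes √(2 + 2r), which is 1.789 at r = 0.6.

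| p | d2/d1 | Difference in units of d1 | Ratio, r = 0 | Ratio, r = 0.6 |
|---|---|---|---|---|
| 1 | 0 | 0 | 0 | 0 |
| 1 | 0.5 | 0.5 | 0.35 | 0.28 |
| 1 | 1 | 1.0 | 0.71 | 0.56 |
| 0.5 | 0 | 0.5 | 0.35 | 0.28 |
| 0.5 | 0.5 | 1.0 | 0.71 | 0.56 |
| 0.5 | 1 | 1.5 | 1.06 | 0.84 |

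**The same in power terms (assumed two-sided alpha 0.05).** With 300 per arm, d1 = 0.229 six-month standard deviations gives 80% power on months 0-6. For the 12-month total, as r goes from 0 to 0.6:
- p = 1, d2 = d1: 51% down to 35%
- p = 1, d2 = d1/2: 17% down to 12%
- p = 1, d2 = 0: only the false-positive rate
- p = 0.5, d2 = d1: 84.5% down to 65.2%

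**The same in visits (assumed b = 3, d1 = -0.6).** Months 0-6: 2.4 against 3.0, difference -0.6, ratio 0.80. Twelve-month totals:
- p = 1, d2 = 0: 5.4 against 5.4, difference 0.0, ratio 1.00
- p = 1, d2 = -0.3: 5.1 against 5.4, difference -0.3, ratio 0.94
- p = 1, d2 = -0.6: 4.8 against 5.4, difference -0.6, ratio 0.89
- p = 0.5, d2 = -0.3: 5.1 against 5.7, difference -0.6, ratio 0.89

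The last two lines show the difficulty. A fully persistent effect with full control response, and a halved later effect with half the control response, give the same arm difference. The total cannot tell them apart.

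**The case against.** The strongest reply is that no planned analysis is harmed. Health care use is not an aim, Section 5.1 names no analysis of visits, and the study calls itself a pilot. That stands, and it limits the point to an ancillary measure. A reader might infer that the abstinence or financial results are compromised; they do not depend on these totals.

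Second, the wording in 4.6.5 is not exhaustive, the abstraction form is not among the documents, and charts could presumably be reviewed again. That also stands: the loss need not be permanent. But nothing in the plan requires a split, and a decision made before abstraction avoids reopening up to 600 charts.

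Third, a reader might infer that the 12-month total can show no programme effect between arms, or that the first-six-month effect always vanishes from it. Neither follows. Randomization makes the total a valid comparison of immediate with delayed offer: if the programme does nothing, the expected difference is zero, so a real difference is evidence of some effect. Full cancellation needs p = 1. Uptake is not given, and controls must still be reached and scheduled at month 6. With p = 0.5, d2 = d1 and independent counts, the total does slightly better than months 0-6 (1.06). If effects on visits come mainly late, the 0-6 month contrast could be the weaker one.

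Fourth, the selection argument covers only some recruitment routes. Newspaper, Facebook and word-of-mouth recruits need no recent visit, the mix of routes is not given, and randomization balances any such fall between the arms. It is a reason to draw no within-arm conclusion, not evidence of bias of known size.

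**Conclusion.** The point holds in a limited form. As described, the post-enrollment visit total cannot isolate the first-six-month effect, because for controls it combines six months before the offer with six months after it. That structural result needs only the schedule in 4.6.2 and the window in 4.6.5. "After the offer" is the accurate description of the second half, since the programme itself lasts 9 weeks.

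How much is lost is unknown. In the tabulated scenarios with independent Poisson counts, relative signal-to-noise runs from 0 to 1.06; positive correlation between the half-years lowers every non-zero value. The 0.35 for p = 1 and d2 = d1/2 is one scenario in that range, not an estimate. The change is worth making because it recovers the clean window for little effort and gives nothing up: the 12-month total is still available by addition.

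**What to change.** In Section 4.6.5, record outpatient and inpatient counts separately for months 0 to +6 and +6 to +12 after enrollment, and keep the 12-month pre-enrollment count as it is. Counts are enough; individual visit dates are optional.

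In Section 5.1, add that the treated-versus-untreated comparison of health care use is the 0 to +6 month count, intervention against control, adjusted for the pre-enrollment count. Report months +6 to +12 and the 12-month total descriptively, labelled as immediate versus delayed offer. State that no effect conclusion will be drawn from before-versus-after change within an arm.

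The cost is a revised abstraction form, a few sentences in 5.1 and slightly more entry per chart, using the same record review. The real downside is a shorter comparison window for inpatient stays, which are likely to be rare; the descriptive 12-month total partly covers that.

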4.7 Staff Participant Interview Recruitment

Staff recruitment procedures were created to minimize staff burden and to ensure we obtain a representative staff sample. We will use two methods of identifying and recruiting potential staff participants:

- (a) Email and phone recruitment: We will request a list of relevant staff (e.g., nurse, physicians at) at each site from clinic and administrative managers. We will send all staff on the list a mass email (Appendix K) to their institutional email address notifying them of the study. The email will include a phone number and email address to contact if they would like to participate or to notify us that they do not want further contact from study staff. The email will inform staff that participation is voluntary and refusing to participate will not affect their employment. For staff who respond indicating they would like to participate, the study's project manager will email or call the staff member at their institutional email or institutional phone number to schedule a time to complete the verbal informed consent process and to conduct the interview. For staff who respond indicating they do not want further study contact, we will remove their name from our recruitment list.

We will send two additional follow ups via email for staff who do not respond to the initial email. The first follow up will be sent one week after the initial email, and the second follow up will be sent one week after the first follow up. Staff who would like to participate will be scheduled for a time to complete an informed consent process and the interview. Staff who refuse participation or whom we are unable to reach will be removed from our recruitment list.

4.8 Staff Participant Interview Consent (Process and Documentation)

We request a waiver of documentation of consent to obtain verbal consent from staff participants. The study coordinator and/or a trained research assistant will obtain verbal consent from each of the staff participants, ensuring that each participant is fully informed of the details of the study and minor potential risks (Appendix O). Additionally, staff will be reassured that their employment will not be affected by their decision to participate or not. Staff who do not wish to participate will have their contact information removed from the study database.

4.9 Staff Participant Interview Procedures

Interviews will be completed in a private room during business hours at a day and time preferred by the staff participant. Using a structured interview guide (Appendix M), the study PI, [name], will ask open-ended questions and follow-up probes that capture staff attitudes and beliefs about the intervention, their feedback on how to improve the intervention, and feedback on how to make it sustainable internally and within other organizations.

5. Data Analysis and Data Monitoring

5.1 Data Analysis

To evaluate the acceptability and feasibility of the integrated intervention, we will calculate the number of counseling sessions completed and satisfaction with treatment, which we will summarize descriptively using count and frequency statistics. We will calculate additional measures of study feasibility and acceptability, including the eligibility rate among people screened, enrollment rate among those eligible, reasons for ineligibility or refusal, and the proportion of participants who would recommend the intervention to other smokers. To estimate the effect of the integrated intervention on outcomes we will use generalized estimating equations (GEE) to model the main effects of time (baseline to 6 and 12 months)

and treatment group, and the interaction of time and treatment, on each outcome. GEE will allow us to determine whether intervention effects are present and whether they change over time.

We will also calculate and sum all time and costs of administering the interventions. Each intervention staff member will record their activity in a web-based intervention tracking system (using REDCap). Staff prospectively input detailed information for a 1-week sample of their activities and associated time required on a monthly basis. Those recording their time and activities have flexibility to add or tailor their entry form to match their exact activities. We will assign a dollar value for each unit of staff time based on the wage and fringe rate of those who perform the activity using regional labor rates from the US Bureau of Labor Statistics. We will also keep track of medications ordered and used by participants, which we will assign a dollar value to using Red Book, a wholesale pharmaceutical pricing index. Once all costs are compiled and summed, they will be adjusted to constant dollars using the medical care component of the Consumer Price Index.

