2.2 Aims

1. Estimate the acceptability of the integrated program and its effect on participants' disposable income, savings, financial stress, mental wellness, and abstinence from cigarettes.
2. Estimate the per-patient cost of the integrated program.
3. Identify barriers and facilitators toward wide-scale implementation of the program model.

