3.5 Eligibility Criteria

3.5.1 Patient participants:

- 1) age ≥ 18 years
- 2) Has smoked a cigarette in the past 30 days, even a puff
- 3) Interested in receiving smoking and financial counseling
- 4) Self-reported income below 200% of the current federal poverty level for a given household composition
- 5) New York City resident
- 6) English or Spanish language
- 7) Able to provide informed consent, and
- 8) Does not have a representative who manages his/her funds (to ensure the participant has the ability to manage household money). We will exclude participants who report being pregnant or breastfeeding (unable to receive NRT).

3.5.2 Hospital staff participants:

- 1) Must be current medical or non-medical provider or administrator at Bellevue Hospital or NYU Lutheran Medical Center

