PHI will be saved and we will only label participants with a pre-screening number. We will also use EPIC to reach out to potential patients using MyChart. We will utilize EPIC's Slicer Dicer research tool to identify NYU Langone-Brooklyn adult patients that are listed as current smokers in EPIC. If a patient has opted in to being contacted about research studies through MyChart, we will send them a notification (Appendix V) about our study through their MyChart portal. Patients will be able to reach out to our study team directly for screening. Patients who are eligible will be scheduled for consent, and patients who are ineligible will be referred to the NY State Quitline.

Fifth, we will recruit participants in-person by approaching patients in primary care clinic waiting rooms. An RA will identify herself/himself as working on a quit smoking research study, ask if the patient would like to hear more, and then provide the patient with a screening questionnaire to assess eligibility, if interested. If the patient does not fit the eligibility criteria, the RA will thank them and move on to the next person waiting for their clinic appointment. If the person is eligible, the RA will describe the study further and ask if the patient would be interested in enrolling. If the patient is interested in enrolling, the RA will escort the patient to a private room, go through the consent process and baseline survey, and randomize the patient.

Participants will also be recruited through word of mouth referrals. Participants can earn a one-time \$20 referral bonus for an eligible person referred and successfully randomized into this study. This referral process will be detailed in the patient's consent form and explained to participants during their in-person consent appointment.

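### For abstinence the plan names no treatment contrast; a logit interaction against baseline would be unidentified or very imprecise if the window is 30 days or more

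*Combined protocol and SAP*

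**What the plan says.** The effect analysis in Section 5.1 (Data Analysis) is a single model specification: "generalized estimating equations (GEE) to model the main effects of time (baseline to 6 and 12 months", then "and treatment group, and the interaction of time and treatment, on each outcome". Baseline is therefore one of the response times for every outcome. The stated purpose is that "GEE will allow us to determine whether intervention effects are present and whether they change over time". No link, working correlation, reference visit or deciding contrast is given.

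Section 2.2 (Aims) lists the outcomes as "disposable income, savings, financial stress, mental wellness, and abstinence from cigarettes". Section 4.4 measures tobacco use at baseline, and Section 4.6.4 says "The surveys will re-assess participant behavior and characteristic assessed at baseline", so a baseline smoking response will exist.

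Section 3.5.1 admits a patient who "Has smoked a cigarette in the past 30 days, even a puff". In Section 4.2, waiting-room recruits move straight from screening to "go through the consent process and baseline survey, and randomize the patient". For patients who telephone, "The RA will schedule eligible participants for an in-person appointment to complete an IRB-approved informed consent process", so some time passes between screening and the baseline survey.

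Section 4.6.2 gives the control arm nothing during the first six months and the full programme after that.

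**The concern.** The entry rule nearly fixes baseline abstinence. With a window of 30 days or more, nobody is abstinent at screening. Only patients who stop between a telephone screen and a later baseline visit could count as abstinent at baseline. A log odds taken from an empty or nearly empty cell is infinite or very noisy, and so is any logit interaction measured against it.

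With baseline as the reference visit, the treatment main effect is the baseline arm difference, and the follow-up effects are carried by the interaction. An analyst who follows Section 5.1 with that coding could report the interaction as the effect on abstinence. The trial is a pilot meant to estimate effects and states no power target, so what is at stake is whether the abstinence estimate comes with a usable interval.

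**Working it through.** **Inputs.** From the document: 300 per arm (Section 2.3); response times baseline, 6 and 12 months (Section 5.1); the entry rule (Section 3.5.1). It gives no quit rates, baseline abstinence, correlation, alpha or power, so there is no planned figure to reproduce. Assumed: complete data, 95% intervals, and 6-month abstinence of 15% vs 8%, 10% vs 5% or 20% vs 10% (17% vs 10% in steps 2 and 3).

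**1. What the coefficient is.** On the logit scale, the 6-month interaction against baseline = log OR at 6 months − log OR at baseline. Randomisation already makes the second term zero in expectation.

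**2. Empty baseline.** With 51/300 vs 30/300 abstinent at 6 months, the direct log OR is ln[(51/249)/(30/270)] = 0.612, with SE √(1/51 + 1/249 + 1/30 + 1/270) = 0.246. Fitting the planned model with no baseline abstainers gave:
- Independence: interaction with model-based SE about 130,000 and robust SE undefined.
- Exchangeable: interaction of 0.76, 1.82 or −5.14 depending on the iteration limit, although the software reported convergence.
- No abstainers in one arm and 2 in the other (independence): −21.9, SE about 4,700.
- The 6-month arm contrast from the independence fit with the empty baseline: 0.612, as it should be.
- Identity link: a finite interaction of 0.070, SE 0.028.

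In three simulated trials (15% vs 8%, empty baseline), the full model with 6 months as reference visit gave arm coefficients of 0.805 (SE 0.269), 0.091 (0.247) and 0.452 (0.248). These equal the follow-up-only results under both working correlations.

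**3. A few baseline abstainers.** Ignoring within-person covariance, the interaction variance is 0.246² + 2[1/k + 1/(300 − k)], with k abstainers per arm.

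| k per arm | Interaction SE | Ratio to 0.246 |
|---|---|---|
| 1 | 1.44 | 5.8 |
| 2 | 1.03 | 4.2 |
| 3 | 0.86 | 3.5 |
| 5 | 0.68 | 2.8 |

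With 1 abstainer in the control arm and 4 in the intervention arm, the baseline log OR is ln[(4/296)/(1/299)] = 1.396. The interaction becomes 0.612 − 1.396 = −0.78, a reversed sign.

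**4. Nearly empty baseline across trials.** P(at least one empty baseline cell) = 1 − [1 − (1 − b)^300]², where b is baseline abstinence. The other columns come from 4,000 simulated trials per setting (latent correlation 0.3), in the order 15/8, 10/5, 20/10, among trials where the interaction is estimable.

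| b | P(empty cell) | Median SE ratio, interaction to direct | Wrong sign |
|---|---|---|---|
| 0.5% | 0.395 | 4.37, 3.57, 4.88 | 18%, 16%, 15% |
| 1% | 0.096 | 3.32, 2.75, 3.67 | 19%, 18%, 17% |

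**5. Shorter window.** With v = 1/[300p(1 − p)], the direct SE is √(v₁ + v₀). The interaction variance is the sum over arms of v₆ + v_b − 2r√(v₆v_b). For 15% vs 8%, the direct SE is √(0.0261 + 0.0453) = 0.267. At b = 2% and r = 0, v_b = 0.170 and the interaction SE is √(0.0714 + 0.3401) = 0.642, a ratio of 2.40. Over the three pairs of rates, b from 2% to 10% and r from 0 to 0.3:
- Largest ratio: 0.631/0.241 = 2.62 (20% vs 10%, b = 2%, r = 0).
- Smallest ratio: 0.358/0.327 = 1.09 (10% vs 5%, b = 10%, r = 0.3).

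Outside that range the order can reverse. At b = 15%, r = 0.5 and 10% vs 5%, the ratio is 0.292/0.327 = 0.89. (For 20% vs 10% at b = 2%, the largest feasible binary correlation is 0.286; this does not affect either extreme.)

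**6. Continuous outcomes.** With equal variances at both visits, change-score variance over baseline-adjusted variance is 2(1 − ρ)/(1 − ρ²) = 2/(1 + ρ). This is 1.54, 1.33 and 1.18 at assumed ρ of 0.3, 0.5 and 0.7.

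**The case against.** The strongest reply is that the plan never commits to the coefficient that fails. The harm needs a logit link, a window of 30 days or more (or a short one with few baseline abstainers), and reporting of the interaction against baseline. Section 5.1 states none of these. Its stated purpose fits equally well with visit-specific arm effects and their change from 6 to 12 months, and both stay estimable. The abstinence window may be in the survey appendices, which are not in the supplied text, so its absence here does not count against the plan. An empty cell would also usually show itself through an absurd standard error.

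Most of this stands, and it rules out three stronger readings that a reader might infer:
- That the planned GEE cannot estimate the effect on abstinence. Step 2 shows that it can: the same model gives the 6-month contrast even with an empty baseline.
- That the interaction is the plan's chosen test, or the only term that can carry the effect. The plan says neither, and with 6 months as reference visit the arm coefficient is the effect.
- That baseline must be removed from the response. Naming the contrast is enough.

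The reply does not remove the point. The plan leaves the choice between a sound contrast and a failing one to the analyst. A warning is not assured, since the software reported convergence on the separated fit. With a handful of baseline abstainers, the output is finite, wide and sometimes of the wrong sign.

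**Conclusion.** The concern holds in conditional form and should be fixed. For abstinence, the interaction against baseline on the logit scale is a poor estimand under this entry rule, and Section 5.1 does not exclude it. With a window of 30 days or more it is unidentified when a baseline cell is empty. At 0.5% to 1% baseline abstinence its interval is about 3 to 5 times as wide as that of the 6-month contrast. With a shorter window the ratio is about 1.1 to 2.6 over the settings examined, but not in every setting (0.89 in one).

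All abstinence rates and correlations are assumptions, with 300 per arm and complete data. That an empty cell breaks the coefficient does not depend on the assumed follow-up rates. The exact agreement between the 6-month contrast and the follow-up-only model was checked with complete data.

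For continuous outcomes such as financial stress, the planned interaction is valid, and only some precision is left unused.

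**What to change.** Add one paragraph to Section 5.1 before outcomes are analysed by arm:
- **Abstinence:** state the window (or cite the survey item), the link and robust standard errors. Name the 6-month between-arm contrast as the treatment effect, because controls receive nothing before then (Section 4.6.2). Obtain it either from a model of the 6- and 12-month responses on arm, visit and arm-by-visit, or as the 6-month arm contrast of the planned model. State that the baseline-referenced interaction will not be used.
- **12 months:** label this contrast as immediate versus delayed treatment.
- **Continuous outcomes (optional):** model the follow-up values with the baseline value already collected (Section 4.4) as a covariate, for the gain shown in step 6.

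This needs no new data, visits or participants. The only cost is the paragraph itself.
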